## 2. Purpose of the Study

The purpose of the study is to evaluate the safety, pharmacokinetics (PK) and pharmacodynamics (PD) of ambrisentan in children with single ventricle heart defects that are undergoing Fontan (stage III) surgical palliation. This is a double blind, placebo controlled study. The primary objective of this Phase I/II study is to assess the plasma PK, safety and PD of oral ambrisentan in children with surgically palliated single ventricle heart defects. A secondary objective will be to assess whether ambrisentan improves post-operative outcomes including amount and duration of chest tube drainage and hospital length of stay.

## 3. Background and Significance

Complex congenital heart defects associated with underdevelopment of a ventricle account for ~8% of congenital heart disease with a birth incidence of 4-8/10000 live births. These single ventricle lesions are associated with high morbidity and 5 year mortality rates that approach 50%. Staged surgical palliation directs returning venous blood flow directly into the lungs so that pulmonary blood flow occurs without the aid of a pumping chamber. The final stage of surgery (stage III – the Fontan procedure) incorporates inferior caval blood flow directly into the pulmonary arteries. Consequently pulmonary blood flow and cardiac output are directly related to pulmonary vascular resistance and ventricular function. The limitations of single ventricle surgical palliation often result in a prolonged post-operative course with pleural effusions a particular concern. There is also continued long term attrition. Elevated pulmonary vascular resistance and impaired systemic ventricular function are important risk factors for early and late failure of single ventricle palliation.

Ambrisentan is an endothelin receptor antagonist that improves pulmonary and possibly systemic endothelial function. Ambrisentan is approved for treatment of pulmonary arterial hypertension in adults and is used off-label for treatment of pulmonary hypertension in children. Children with single ventricle heart defects demonstrate both pulmonary and systemic endothelial dysfunction and may benefit from treatment with this drug. However pharmacokinetics and hemodynamic efficacy of ambrisentan have not been studied in single ventricle patients. The most widely used alternative agent, sildenafil, was recently associated with increased mortality in children. There is now an FDA safety warning against use of sildenafil in children. We have previously demonstrated hemodynamic benefits with use of sildenafil in these patients but ambrisentan is a potentially safer agent. Therefore this study would fill an unmet need to guide dosing and evaluate efficacy of ambrisentan in this vulnerable population.

## 4. Design and Procedures

This is a single-center, randomized, blinded PK study of ambrisentan in children ages  $\geq 24$  months and  $\leq 120$  months with single ventricle anatomy. There will be up to 20 subjects enrolled; 16 will receive ambrisentan and 4 will receive placebo. A small placebo control group is warranted to ensure that any treatment effect is not a result of post-operative improvement. Patients will be enrolled at the time of their routinely scheduled Fontan surgery.

**Initial Dose:** Oral ambrisentan 2.5 – 5 mg, single dose, once daily (nasogastric and gastrostomy tube administration will be considered only when a nasogastric or gastrostomy tube is already in place as part of routine post-operative care). Subjects will be randomized by Investigational Drug Services (IDS) to placebo (n=4) or oral ambrisentan (n=16) using permuted blocks. Subjects will receive either an oral suspension (2.5 or 5mg) or a 5mg tablet depending on their ability to swallow a tablet. To begin to ensure safety, the initial 5 subjects enrolled in the study (at least 4 active drug) will receive a dose of 2.5mg in a liquid suspension prepared by IDS. After enrollment of these subjects we will perform a preliminary PK/safety analysis and evaluate ambrisentan exposure. If the drug is well tolerated (no grade III or greater adverse events) and exposure is less than the target exposure of 500-800ng/mL, then we may increase the dose to 5mg/dL provided via tablet in those able to take a tablet or suspension for all others. If drug exposure is less than 100ng/mL then we will enroll additional study subjects to ensure that at least 16 study subjects achieve adequate drug exposure. If drug exposure is in the target range then we will continue to enroll study subjects to receive the 2.5mg suspension.

As summarized below, study drug will be discontinued for any grade 3 or greater adverse event. If this occurs then IDS will be permitted to unblind the study patient to allow for appropriate adverse event reporting. Drug administration will start on post-operative day #1 with initiation of oral feeds. Study drug/placebo will be prepared and delivered to the patient bedside by investigational drug services and administered orally. Subjects will continue on study drug for 3 days.

The total study duration is expected to be approximately 24 months for enrollment of up to 20 subjects. Study participants will remain in the study until 1 month after discharge following stage III surgery intervention or for 6 months – whichever is shorter. The subjects will receive routine care before, during and immediately after surgery and after hospital discharge. We will record all in-hospital adverse events and tabulate by organ system. One month after the last study drug administration (dose #3), we will contact patients by phone or evaluate in person if they remain hospitalized.

Plasma PK will be evaluated using a limited sampling scheme. A preliminary safety and PK analysis will be performed after 5 subjects are enrolled. Ambrisentan PK will be evaluated and dosing may be adjusted to achieve levels consistent with those reported in the adult and pediatric literature.

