**NCT02080637**

**Document Date: March 21, 2016**

**Title: Safety, Pharmacokinetics (PK) and Hemodynamic Effects of Ambrisentan in Single Ventricle Pediatric Patients.**

**1. Protocol Synopsis**

|   |  |
|---|--|
| Protocol Title                     | Safety, Pharmacokinetics (PK) and Hemodynamic Effects of Ambrisentan in Single Ventricle Pediatric Patients.  |
| Product                            | ambrisentan  |
| Objective:                         | To evaluate the safety, PK and hemodynamic effect of ambrisentan in pediatric patients with single ventricle heart defects.  |
| Study Design:                      | Randomized, double blind, placebo controlled PK, safety, and hemodynamic efficacy study.   |
| Study Population:                  | Up to 20 patients ages $\geq$ 24 months and $\leq$ 120 months with single ventricle cardiac lesions; Undergoing elective Fontan surgical palliation.   |
| Number of Subjects:                | Up to 20 subjects  |
| Duration of Subject Participation: | Until 1 month after administration of the last study drug administration   |
| Inclusion criteria                 | 
 
1. Age <math>\geq</math> 24 months; <math>\leq</math>120 months.
 
2. History of congenital heart disease with severe hypoplasia of a right or left ventricle.
 
3. Undergoing Fontan surgery as part of standard clinical care.
 
4. Availability and willingness of the parent/legally authorized representative to provide written informed consent and, as appropriate, assent from the child.
 
  |

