### **Study Procedures**

1. Record the start and stop time of ambrisentan administration and all concomitant drugs.
2. Hemodynamic evaluation performed during pre-operative cardiac catheterization (obtained as part of usual clinical care), prior to initiation of study drug, and at 0-1,1-6,18-30 and 40-60hrs after administration of the first ambrisentan dose (blood samples will be collected only if central monitoring lines remain or if they can be timed with a routine lab collection)

- a. Record Fontan, common atrial, and systemic arterial pressures from existing central lines that are placed as part of routine post-operative care.
- b. Collect study labs (coincident with scheduled PK levels – see below):
  - i. plasma samples for biomarkers (endothelin 1 [ET1], brain natriuretic peptide [BNP]).
- c. Record oxygen saturation from routinely collected arterial and venous blood gases.
- 3. PK blood samples (500 µL, up to 7 per patient) and pressure measurements will be obtained at baseline and at 1–2, 3–4, 5–6, 8–12, 12–16, 24, and 48 hours post-initial drug administration.
- 4. Adverse events will be collected during and for 1 month after the last study drug administration. Results will be tabulated by organ system.
- 5. Physical examination will be performed within 24 hours after administration of study drug and once daily during study enrollment.
- 6. Record all AEs and SAEs.
- 7. Record all concomitant medication administered 24 hours after administration of study drug.
- 8. Up to 4 scavenge samples will be obtained from the clinical laboratory from samples collected in the 24 hours following ambrisentan administration. Scavenged samples are left over heparinized plasma samples from these children that are collected from the clinical laboratory prior to discarding.

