### **Hospitalization Procedures**

- 1. Any of the following clinical laboratories performed as standard of care during the study will be recorded. We will use the laboratory values closest to study dose if there have been multiple tests.
  - a. Hematology: hematocrit, hemoglobin, white blood cell count with differential, platelet count
  - b. Serum chemistry: creatinine, blood urea nitrogen, sodium, potassium, calcium
  - c. Liver function tests: aspartate transaminase (AST), alanine transaminase (ALT), alkaline phosphatase, total bilirubin, conjugated bilirubin
- 2. Physical examination will be performed daily during the post-operative hospitalization.
- 3. Record all AEs for 24 hours after the last dose of study drug
- 4. Record all SAEs for 1 month after the last dose of study drug
- 5. Record duration of mechanical ventilation
- 6. Record hospital length of stay
- 7. Record intensive care unit length of stay
- 8. Record duration and volume of chest tube drainage

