## **Safety**

Adverse events will be collected during study participation.

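### The protocol gives two ends of participation and several adverse-event windows that cannot all be followed, so event counts have no defined common time base

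*Combined protocol and SAP*

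**What the plan says.** Two rules say when a child leaves the study.

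- Synopsis, duration of participation: "Until 1 month after administration of the last study drug administration".
- Section 4: "until 1 month after discharge following stage III surgery intervention or for 6 months", whichever is shorter. The start of the six months is not given.

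Four places say how long adverse events (AEs) are collected.

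- Section 14, Safety: "Adverse events will be collected during study participation". This takes whichever definition of participation is in force.
- Section 4: "We will record all in-hospital adverse events and tabulate by organ system". The same paragraph plans a contact one month after dose 3, by phone or in person for a child still in hospital.
- Section 10, Study Procedures, item 4: "Adverse events will be collected during and for 1 month after the last study drug administration".
- Section 10, Hospitalization Procedures, item 3: "Record all AEs for 24 hours after the last dose of study drug". Item 4 extends serious adverse events (SAEs) to one month after the last dose.

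Section 14 defines an SAE as any event of grade 3 or higher, so the 24-hour rule governs grades 1 and 2. Section 2 lists safety within the primary objective and makes "post-operative outcomes including amount and duration of chest tube drainage and hospital length of stay" the secondary objective.

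**The concern.** Safety is part of the primary objective, and an AE count means little unless one knows how long each child was observed. Here that depends on which section the study team follows.

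Two consequences matter. First, both Section 4 rules (in-hospital events, or participation to one month after discharge when read with Section 14) tie observation to the discharge date. Hospital stay is something the drug is hoped to shorten. A child who stays longer is watched longer and has more chance of a recorded event, so a difference in stay between arms would appear partly as a difference in AE counts. Second, the 24-hour rule would drop almost all post-treatment grade 1 and 2 events that the one-month rule would keep. Two people abstracting the same chart could each follow the protocol and produce different AE tables.

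**Working it through.** The plan states no figure to reproduce. The check sets the rules on one calendar.

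**Inputs from the protocol**
- First dose on post-operative day (POD) 1; once daily for 3 days (Section 4). Last dose on POD 1 + 2 = 3 if no dose is missed or delayed.
- The participation and AE rules listed above.

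**Assumptions**
- 1 month = 30 days; 6 months = 183 days counted from surgery.
- Discharge on POD D, with D = 7, 14 and 30 as examples. The documents give no length-of-stay distribution.

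**Formulas, in days after the last dose**
- Synopsis participation, Study Procedures item 4, and SAEs under Hospitalization Procedures item 4: 30 (ends POD 3 + 30 = 33).
- Section 4 participation: min(D + 30, 183) − 3.
- Section 4 in-hospital events: D − 3.
- AEs under Hospitalization Procedures item 3: 1 (ends POD 3 + 1 = 4).

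| Rule | D = 7 | D = 14 | D = 30 |
|---|---|---|---|
| Synopsis; Study Procedures item 4; SAEs in item 4 | 30 | 30 | 30 |
| Section 4 participation | 37 − 3 = 34 | 44 − 3 = 41 | 60 − 3 = 57 |
| Section 4 in-hospital | 7 − 3 = 4 | 14 − 3 = 11 | 30 − 3 = 27 |
| 24-hour rule (non-serious AEs) | 1 | 1 | 1 |

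The two participation rules agree only if D + 30 = 33, that is, discharge on the day of the last dose. The six-month cap binds only when D + 30 > 183, a stay beyond 153 days, so in practice it does not limit the dependence on stay.

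**How a difference in stay would reach the AE table.** Take Section 4 participation as the window, counted from the first dose: D + 30 − 1. With assumed stays of 14 days on placebo and 10 on ambrisentan, the windows are 43 and 39 days. At the same constant event rate in both arms, ambrisentan would show 39/43 = 0.907 as many events per child, about 9% fewer, with no true difference. Other assumed pairs (placebo/ambrisentan):
- 14/12 days: 41/43 = 0.953, 5% fewer.
- 10/7 days: 36/39 = 0.923, 8% fewer.
- 21/14 days: 43/50 = 0.860, 14% fewer.

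These show the mechanism only. If events cluster soon after surgery, the effect through this rule would be smaller.

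**The case against.** The strongest reply is that the procedural text already fixes the window. Study Procedures item 4 and the SAE item both count one month from the last dose, and the only follow-up contact is placed at that point; none is scheduled one month after discharge. A reader might infer that the plan's working AE window depends on hospital stay. The documents do not establish that: it is one available reading, resting on Section 4 alone or with the single sentence in Section 14. This part of the reply stands. It does not remove the conflict, because Hospitalization Procedures item 3 contradicts Study Procedures item 4 directly, and the in-hospital rule in Section 4 differs from both.

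A reader might also infer that the synopsis rule truncates hospital stay and chest-tube duration at about POD 33 in the sickest children. The documents do not support this. Hospitalization Procedures items 5 to 8 record ventilation, hospital and intensive-care stay, and chest-tube drainage with no cutoff, while the AE and SAE items in the same list have one. Section 4 also expects some children to be in hospital at the one-month contact.

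Nor should 34, 41 and 57 days against 30 be read as the size of a bias. They are days of participation for single children at assumed discharge days, not a comparison of arms.

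Finally, the analysis is descriptive, no between-arm AE test is specified, and placebo has 4 children against 16. Dosing lasts 3 days, and Section 5 cites a 7.6-hour half-life, so the disputed weeks lie well after exposure. That is fair and keeps the point minor, but a descriptive AE table still needs a stated period of observation.

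**Conclusion.** The inconsistency is real and in current text: two ends of participation, and AE rules that run to 24 hours after the last dose, to discharge, to one month after the last dose, or to the end of a participation period that is itself defined in two ways. Where Section 4 is followed, the window lengthens with a secondary outcome and AE counts are not on a common time base. Where Hospitalization Procedures item 3 is followed, recording of grade 1 and 2 events ends at about POD 4.

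The size of any bias cannot be computed from the documents. The calendar results assume three doses on schedule, a 30-day month and the chosen discharge days; the 5% to 14% illustrations also assume a constant, equal event rate. This is a minor point of internal consistency that is worth correcting because the correction is nearly free.

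**What to change.** 1. Reconcile the synopsis, Section 4, both procedure lists in Section 10, and the Safety paragraph of Section 14 to one AE and SAE window, counted from the last dose and the same for every child. One month matches the synopsis, Study Procedures item 4, the existing SAE item and the contact already planned in Section 4. Amend Hospitalization Procedures item 3 as well; aligning only the synopsis with Sections 4 and 14 would leave the 24-hour conflict in place.
2. Tabulate AEs by arm within that window, and list any later in-hospital events separately.
3. State that hospital stay and chest-tube outcomes are recorded to discharge regardless of the AE window, up to the six-month limit, and define when the six months start. Treat a child still in hospital at that limit as censored.
4. If some children have already been followed under the 24-hour rule, say so beside the table, since their later grade 1 and 2 events may be missing.

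The cost is a wording amendment with no added visit. The one downside is that late in-hospital events fall outside the main AE table, which the separate listing covers.

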## 5. Study medication

### Rationale for Dose Selection

Preliminary data from 16 children with pulmonary hypertension using once-daily doses of 5 mg demonstrate similar  $C_{max}$  and  $AUC_{24hr}$  to those seen in adult patients. This PK study included children and adolescents ages 2 years – 18 years including 9 subjects age  $\leq 10$  years. Weight ranged from 13kg to 52 kg. The half-life of elimination was 7.6 hours (range 5.4–15.3 hours), and there was improvement in hemodynamic parameters (mean pulmonary arterial pressure  $55\pm 18$  mm Hg decreased to  $45\pm 20$  mm Hg after initiation of ambrisentan,  $p=0.04$ ). Ambrisentan was well tolerated in all patients with no serious adverse events. In post-operative Fontan patients, I anticipate decreased bioavailability due to post-operative bowel wall edema but also decreased hepatic elimination. I will perform a preliminary PK/PD analysis after enrolling the first 5 subjects (at least 4 active drug) and adjust the dosing to achieve target peak concentrations of 500–800 ng/mL, a range that has demonstrated therapeutic efficacy as well as safety in adults. To maintain blinding, we will request that ambrisentan levels be sent from the commercial

laboratory directly to IDS. IDS will remove study patient identifiers and then forward the drug levels for PK analysis and determination of dose adjustment.

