### Compounding:

- All drug compounding procedures should be performed under a safe fume hood.
- During preparation of suspension, gloves and a mask should be worn.
- Crush 5mg tablet,
- Suspend in equal parts of Ora-plus (2.5 mL) and Ora-sweet (2.5 mL)
- Stability: the suspended dose must be administered within 4 hours of preparation.

Ambrisentan must be delivered to the patient room from the investigational drug service on the day of administration. A label containing the protocol number and patient number must be applied to the drug package or syringe. The exact time of study drug administration must be documented on the case report form. Vital signs will be recorded per standard post-operative protocol for the remainder of the study.

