### **Plasma PK Sampling and Handling**

Timing of samples will treat the start time of oral administration of the first dose as time zero (0). The date and time will be recorded for the start/stop time of oral drug administration and for the acquisition time of the PK sample. The pharmacokinetic samples will be obtained in sodium heparin collection tubes.

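### Removing identifiers does not fit an interim PK/PD analysis of five children run by the investigator: the levels show treatment, and the PK/PD join needs the link that was removed

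*Combined protocol and SAP*

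**What the plan says.** Section 5 (Rationale for Dose Selection) sets out the interim in the first person: "I will perform a preliminary PK/PD analysis after enrolling the first 5 subjects", with no fewer than four of the five on ambrisentan. On the blind it says: "To maintain blinding, we will request that ambrisentan levels be sent from the commercial" laboratory straight to IDS, after which "IDS will remove study patient identifiers and then forward the drug levels for PK analysis and determination of dose adjustment". No other safeguard is named, and no analyst outside the blinded team.

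Section 4 randomizes "to placebo (n=4) or oral ambrisentan (n=16) using permuted blocks", without a block size. It describes the same interim differently: "we will perform a preliminary PK/safety analysis and evaluate ambrisentan exposure". The later summary in section 4 also speaks only of safety and PK.

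On times, section 10 (Plasma PK Sampling and Handling) states: "The date and time will be recorded for the start/stop time of oral drug administration and for the acquisition time of the PK sample". Section 5 (Compounding) adds: "The exact time of study drug administration must be documented on the case report form". Section 10 (Study Procedures) schedules pressure measurements together with the PK samples. Section 13 specifies non-compartmental analysis.

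The documents do not say whether actual or nominal times, or any pressure data, go with the forwarded levels. Nor do they say whether IDS withholds placebo results.

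**The concern.** Removing a name protects the blind only if what remains does not reveal treatment. Here what remains is the plasma concentration of the study drug. The recipient is the person running the interim, and there are only five profiles to place. The safeguard therefore rests entirely on the recipient being unable to tell which child each profile belongs to, while a PK/PD analysis requires exactly that knowledge.

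The placebo group has only four children and exists, according to section 4, to separate a drug effect from ordinary recovery after surgery. Someone who knows the allocation may judge differently whether an adverse event is drug-related (section 14). Chest-tube drainage and hospital stay, the secondary outcomes in section 2, depend partly on clinical decisions.

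**Working it through.** **Inputs.** Interim of 5 children, at least 4 active (sections 4 and 5); allocation 16:4 in permuted blocks (section 4); half-life 7.6 h, range 5.4 to 15.3 h (section 5); low-exposure mark 100 ng/mL (section 4; section 13 prints ng/dL); prior ambrisentan excluded within 48 h (section 6); 1-hour sampling windows at 1–2, 3–4 and 5–6 h (section 10). Assumptions not in the documents: block size, a peak at 2 h with first-order decay, and sample times spread evenly and independently within windows.

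**1. The plan's figure.** Expected active among five = 5 × 16/20 = 4, which agrees with the plan's minimum of 4. Whether a placebo child is among the five depends on block size (hypergeometric counts):

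| Block (active:placebo) | P(0 placebo) | P(1 placebo) | P(at least 4 active) | P(1 placebo, given at least 4 active) |
|---|---|---|---|---|
| 5 (4:1) | 0 | 1.000 | 1.000 | 1.000 |
| 10 (8:2) | 0.222 | 0.556 | 0.778 | 0.714 |
| 20 (16:4) | 0.282 | 0.470 | 0.751 | 0.625 |

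Of these three, only blocks of 5 guarantee the plan's minimum, and they always give exactly one placebo child.

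**2. Do levels show treatment?** Level at time t = peak × 2^(−(t − 2)/half-life). With a peak of only 100 ng/mL and the shortest half-life, 5.4 h:
- at 6 h: 100 × 2^(−4/5.4) = 60 ng/mL
- at 12 h: 100 × 2^(−10/5.4) = 28 ng/mL

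At 7.6 h the values are 69 and 40 ng/mL. The fraction of an earlier level remaining after 48 h is 2^(−48/7.6) = 1.3%, or 2^(−48/15.3) = 11% at the longest half-life. A placebo profile would therefore be at or near zero. No assay limit is given, so it should be described as below the limit, not as zero.

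**3. The join.** A PK/PD analysis pairs each level with the same child's pressure at that time. Levels without any link cannot be paired. If IDS paired them under a dummy code, the pressures would themselves identify the child, because the study team records them. Either way, the safeguard and the analysis do not fit together.

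**4. If actual times are forwarded.** The chance that one child's time pattern is unique among five = (1 − 1/m)^4, where m is the number of possible patterns.
- 1-minute resolution, one window: m = 60, (59/60)^4 = 93%
- 5-minute rounding, one window: m = 12, (11/12)^4 = 71%
- 5-minute rounding, three windows: m = 12³ = 1,728, 99.8%

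Guessing gives 1/5 = 20%. This step is conditional, since the plan does not say that times are forwarded.

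**5. No placebo child among the five.** All five profiles are then drug-positive, and all five children are known to be active with no matching.

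**6. Size.** 5/20 = 25% of children; 1/4 = 25% of placebo children if one is among the five. Identifying that child also shows the other four to be active.

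**The case against.** The plan says only that levels are forwarded. Levels with nominal times and no link to pressures would hide which child is which whenever one of the five is on placebo. PK/PD appears as a description of the interim only in section 5; section 4 twice limits it to PK and safety, and its dose rule uses exposure and tolerability alone. Treatment lasts 3 days and the line-based hemodynamic schedule ends by 60 hours, so most of both is finished before levels come back. IDS may already unblind after a grade 3 or greater event. The planned statistics are descriptive, with no between-arm test.

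Much of this stands and limits the reach. A reader might infer that recorded clock times travel with the levels, that a placebo child is certain to be among the five, that decisions to stop study drug are widely biased, or that the interim unmasks children enrolled later. The documents do not support these. Forwarding of times is likely for non-compartmental analysis but not stated; zero placebo children is allowed; dosing is mostly over; and nothing in the five profiles identifies a later child.

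The mismatch itself remains. Section 5 names the PK/PD analysis, its author as the analyst and identifier removal as the only safeguard, all in one paragraph. Nominal times would not repair the PK/PD join, and would not help if all five are active. Descriptive summaries can still be biased by unblinded attribution.

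**Conclusion.** The concern holds in a limited form. The stated safeguard does not fit the stated interim analysis, which is more than missing detail. It affects at most 5 of the planned 20 children and probably 1 of 4 placebo children: given at least 4 active, the chance that one is included is 63% to 100% over the block sizes tried. The exposure falls mainly on adverse-event attribution, chest-tube and stay outcomes, and what remains of follow-up, chiefly for the most recently enrolled children. How long attribution stays open is itself unclear: section 10 gives 1 month for adverse events under Study Procedures, but 24 hours for adverse events and 1 month for serious ones under Hospitalization Procedures.

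The conclusion assumes that the first-person author belongs to the blinded team and that active children absorb measurable drug. An active child with almost no absorption could be mistaken for placebo. Section 13's aim of at least 16 children above a peak threshold suggests that levels are also reviewed after the interim, so the gap may extend past the first five; the plan does not describe that review.

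**What to change.** - State who receives the levels, with what data, and that this party is outside the blinded team. IDS, or a named PK analyst, should hold the individual levels and return only a summary of active-arm exposure (for example geometric mean and range) or its category under the section 4 exposure rule.
- Leave out the number of children. Individual active values would still reveal that all five are active if five were sent.
- Make the interim PK/safety only and reconcile section 5 with section 4. Link levels to hemodynamics after database lock and unblinding.
- Use the same routing for any later review of levels toward the section 13 count of 16.

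The cost is about a paragraph of text and a small amount of extra work for the unblinded party. If IDS does not do PK calculations, an analyst has to be named. The interim loses its PK/PD view, which the dose rule does not use.
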